1.0 Objectives

1.1 Describe the purpose, specific aims, or objectives of this research.

Response: The purpose of this study are to determine the effectiveness of the daily report card (DRC) approach to supporting children with ADHD in special education in schools compared to a business as usual condition. Children in the study will be randomly assigned (like flipping a coin) to business as usual, or to treatments that increases, if needed, across the school year. All children will have progress carefully monitored across the school year.

The objective is to observe whether the addition of the DRC approach is superior to special education procedures as usual .

1.2 State the hypotheses to be tested, if applicable.

NOTE: A hypothesis is a specific, testable prediction about what you expect to happen in your study that corresponds with your above listed objectives.

Response:

Aim 1. Investigate the efficacy of using a DRC mechanism to link the child with ADHD's IEP to daily classroom behavior.

Hypothesis 1. Children who have a DRC linked directly to their IEP goals and objectives will exhibit better classroom behavior and exhibit better academic productivity outcomes than children who receive school as usual (SAU) in which an IEP has been developed but has not been enhanced through use of a DRC. Children who have a DRC will also demonstrate better outcomes on measures of IEP goal attainment, school functioning, and academic progress.

Aim 2. Investigate moderators of treatment outcome.

Hypothesis 1. It is hypothesized that grade level will moderate intervention effects. It is hypothesized the DRC intervention will be more effective in the primary grades (i.e., K-3) relative to intermediate grades (i.e., 4-6) as the less complex class schedule and academic demands (e.g., fewer long-term assignments; fewer organizational demands on the student) will facilitate greater adherence and implementation and therefore better outcome.

Hypothesis 2. It is hypothesized that the presence of ADHD + comorbid aggressive/oppositional behavior (i.e., comorbid disruptive behavior disorders; DBD) will moderate intervention effects. Specifically, it is hypothesized that the DRC intervention will be more effective for children with comorbid DBD because they will have increased classroom/social impairment and therefore more opportunity to exhibit improvement.

Hypothesis 3. It is hypothesized that IEP quality will moderate intervention effects. Specifically, it is hypothesized that the DRC intervention will be more effective for children with low-quality IEPs as its use will serve to scaffold poorly constructed or incomplete IEP goals/objectives.

Aim 3. Investigate mediators of treatment outcome

Hypothesis 1. As we outline in our logic model below, the fidelity of implementation ([name] et al., 2014), which includes improved positive teacher-child interactions, increased frequency/consistency of feedback, and enhanced home-based contingency management are all thought to be enhanced through the intervention and will mediate improvement in functional domains. These indicators will be investigated individually as mediators as well as jointly.

2.0 Scientific Endpoints

2.1 Describe the scientific endpoint(s), the main result or occurrence under study.

*NOTE: Scientific endpoints are outcomes defined before the study begins to determine whether the objectives of the study have been met and to draw conclusions from the data. Include primary and secondary endpoints. Some example endpoints are: reduction of symptoms, improvement in quality of life, or survival. Your response should **not** be a date.*

Response:

Primary scientific endpoints are blinded observations of classroom behavior collected at the end of the school year and teacher ratings on the Disruptive Behavior Disorders Rating Scale, Impairment Rating Scale, Academic Performance Rating Scale, and BASC-2 rating scale. Teachers will also complete a rating of IEP goal attainment at the end of the school year.

Secondary outcome measures include assessments of academic achievement, classroom functioning, impairment, parent and teacher satisfaction with treatment, and student-teacher relationship.

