In the proposed study, the efficacy of the DRC as an enhancement to children with ADHD’s IEPs will be investigated in an experimental study. Children will be randomly assigned on the individual level to a condition where a behavioral consultant works with the child’s teacher(s) to construct a DRC, implement it, and monitor it, or to an IEP only, school as usual (SAU) condition, where teachers will attempt to meet the IEP goals and objectives as they typically would. A DRC is an operationalized list of target behaviors (e.g., “completes reading assignments with 80% accuracy or better,” “has no office time outs during the day”) that are evaluated each day by the teacher. The DRC is used as a means of providing the child and parent feedback on progress on a daily basis, and it doubles as a mechanism teachers can use to track and monitor the

child's behavior and progress on key functional domains. The DRC can be easily linked to IEP goals and objectives, providing a bridge between the IEP and the child's daily functioning in the classroom. Parents will also be taught in parenting meetings how to reward their child at home for successful attainment of DRC goals and how to communicate effectively with their child's teacher.

Measures of key outcomes will include observations of behavior in the classroom conducted by observers naïve to group assignment or study hypotheses, academic performance outcomes, parent and teacher ratings of functioning, and IEP goal attainment. Primary measures of outcome will be analyzed using ANCOVA procedures. Secondary measures will include teacher ratings of ADHD and disruptive behavior/impairment. Additional analyses will investigate moderators (grade level, comorbid aggressive behavior, IEP quality). It is further hypothesized that classroom environment and fidelity of implementation at school/home will mediate outcomes (i.e., classroom climate, the fidelity of teacher monitoring/feedback regarding behavior, consistency of parent-implemented consequences at home).

[figure not shown]
3.2 Include complete citations or references.

Response: Response: None included (see grant application for expanded background, preliminary studies, and references)

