Measures will be used that capture the domains of functioning important for children with ADHD classified as students in need of special education. Therefore, measures will span aspects of behavioral and academic functioning in the school setting and use multiple sources (child, observer, teacher, and parent). Below we describe measures of these relevant study outcomes as well as information on the reliability and validity of the selected measures. Although sometimes implemented in studies of ADHD treatment (AACAP, 2007), we elected not to require that students be taken off medication for the study duration for practical and ethical reasons; our block randomization approach for the medication variable addresses this issue.

Primary Measures of Behavioral Functioning.

Observations of Classroom behavior. Independent observations will be conducted using the Student-Behavior Teacher-Response observation system (SBTR; [name], Greiner, & Gnagy, 2008; Vujnovic, [name] et al., 2014). The SBTR is an observation code that collects information on: (1) the frequency of student rule violations; (2) whether a teacher observed the misbehavior; (3) if observed, the teacher consequence employed and whether it was an appropriate consequence. The SBTR system also records the number of praise statements and commands issued. The SBTR is a well-defined and validated observation system for use with children with ADHD in classroom settings. The SBTR system documents child functioning across a number of disruptive behavior categories (e.g., be respectful, obey adults, work quietly, stay on task), and it is consistent with an evidence-based assessment procedure for ADHD ([name], [name], & Massetti, 2005). It represents the evolution in a well-established observational code, as it is a modified version of the behavioral observation code used in the analogue classroom studies noted above (Atkins, [name], & Licht, 1985, 1988, 1989; [name] et al., 2007; [name] et al., 1993), as well as including the procedures used in the STP

classrooms to measure teacher fidelity to behavior management ([name], [name], et al., 2005; [name] & Hoza, 1996).

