The SBTR has been successfully employed as a primary outcome in our Goal 2 project ([name], Vujnovic et al., 2010; see preliminary study 2), along with two other IES-funded projects, one a between-group study of school-wide social and character development programs ([name], P.I., <http://www.sacdprojects.net>), and the other a study designed to investigate the best dose and sequencing of school-based treatments for children with ADHD ([name], P.I., R324B06045). The SBTR observation system has good inter-rater reliability – the mean difference between the observers on total rule violations recorded was 1.8 (SD=2.3; Range=0-12). For the total rule violations variable, the correlation between the two observers was .96 (p < .001), supporting the inter-rater reliability of the observation measure. The SBTR observation system also demonstrated moderate correlation with the DRC recorded by the teacher (r= -.46), suggesting the half-hour observation relates in the expected manner to the DRC completed over an entire school day ([name], Vujnovic, et al., 2009).

The SBTR observations will occur on three separate days in the month of January (before intervention begins) and three separate days in the month of May for each child. Each observation will last for thirty minutes. Time of day and activity will be controlled. Observers will be blind to the child's treatment condition. To ensure the reliability of this measure, 20% of observations will be completed simultaneously with a second observer to allow the calculation of estimates of reliability. Please see the Table in the Treatment Integrity section below for how these observations are independent and distinct from the integrity observations.

Teacher ratings of behavior. Teachers will be administered the following measures during the first two weeks of the month of January and again in May. The following measures will be used as indicators of student outcomes as secondary measures to the primary observational measure.

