At the endpoint assessment, teachers will complete impressions of improvement on each of the child's academic and socially related IEP goals and objectives with those unrelated to social or academic outcomes, such as fine motor or speech goals, removed (Guy, 1976; [name] et al., 2000). This measure will ask teachers to rate improvement on each goal/objective at the end of the school year on a seven-point Likert scale (Very much worse to Very much improved; the midpoint indicates No change). Thus, scores can range from 1.0-7.0. Scores will be averaged across items to provide an overall index of improvement at post-treatment. Ratings of improvement have long been used in numerous pharmacological and behavioral treatment studies. This scale has been shown to be sensitive to behavioral treatment effects in Summer Treatment Program classrooms ([name] & Hoza, 1996; [name] et al, 2000), parent training interventions ([name], Chacko, et al., 2009), our Goal 2 Study ([name], Vujnovic, et al., 2010), and a randomized trial of a school-wide behavioral intervention ([name], Massetti, et al., 2007). The global improvement rating has demonstrated inter-rater reliability (e.g., Tolin et al., 2007; $r = .81$), and clinician-rated improvement scores correlate with parent reports of improvement for individualized target behaviors (Arnold et al., 2003).

Primary Measures of Academic Functioning.

Academic Performance Rating Scale (APRS). The APRS is a 22-item measure that asks teachers to rate different aspects of a child's academic performance in the classroom (DuPaul, Rapport, & Perriello, 1991). The APRS (DuPaul et al., 1991) includes an Academic Productivity factor (7 items) that relates to work completion and accuracy, independent work, and following directions (coefficient alpha = .94; test-retest reliability over two weeks = .93), an Academic Success (12 items) factor related to the child's academic achievement, recall, and ability (coefficient alpha = .95; test-retest reliability over two weeks = .91).

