Specifically, each outcome score will be regressed on the corresponding pre-test score, a treatment indicator, and four covariates (medication status, grade level, comorbid DBD, and child gender)—the first three of which will be evaluated as potential moderators of treatment in Aim 2. Although the pretest score can be conceived as simply another covariate, it is distinguished here to emphasize the point that its inclusion results in improved statistical power relative to a repeated measures approach for evaluating treatment efficacy (Van Breukelen, 2006). Group differences on adjusted post-test scores (i.e., the significance test of γ_2) will inform the efficacy of using the DRC to enhance academic performance and behavioral outcomes beyond that associated with the routine use of IEP. Measures of primary outcome will be observations of classroom behavior and teacher ratings of academic performance. Measures of secondary outcome will include teacher ratings of symptoms and impairment related to ADHD.

Aim 2. Investigate moderators of treatment outcome.

Aim 2 will be evaluated by extending the ANCOVA model from Aim 1 as follows

$$\gamma_{post}$$

[figure not shown]
$$= \gamma_1 pretest + \gamma_2 DRC + \sum_{j=1}^2 \gamma_j covs \\ + \sum_{k=1}^3 \gamma_k moderator + \gamma_k moderator * DRC + e_i$$

Specifically, Aim 2 will extend the models estimated from Aim 1 by including three additional terms (i.e., the product of each of the three moderators—age group, comorbid DBD, IEP Quality—with the indicator of treatment). Tests of each of these three terms (i.e., $\gamma_{k1}, \gamma_{k2}, \gamma_{k3}$) will inform Aim 2. Each DRC X moderator term that is statistically significant will be probed using simple main effects (i.e., comparisons between DRC and SAU outcomes within each level of the moderator variable) in order to delineate the differential magnitude of treatment on adjusted post-test scores as a function of a given covariate (i.e., primary vs. secondary grade; ADHD only vs. ADHD+DBD; High Quality vs. Low Quality IEP).

Aim 3. Investigate mediators of treatment outcome. Aim 3 will be evaluated using a path analytic approach for testing mediation. The path model will extend the ANCOVA models above by simultaneously

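### Section 2.1 makes teacher symptom and impairment ratings primary, sections 3.1, 10.2 (text) and 17.1 make them secondary, and nothing says which section governs

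*Combined protocol and SAP*

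**What the plan says.** Four sections of the combined protocol and SAP assign tiers to the outcome measures.

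- **Section 2.1.** Primary: blinded end-of-year classroom observations and "teacher ratings on the Disruptive Behavior Disorders Rating Scale, Impairment Rating Scale, Academic Performance Rating Scale, and BASC-2 rating scale". A teacher rating of IEP goal attainment is added in the same paragraph without a clear tier. The next paragraph reads "Secondary outcome measures include assessments of academic achievement, classroom functioning, impairment" and goes on to satisfaction and the student-teacher relationship, so impairment also appears as secondary, with no instrument named.
- **Section 3.1.** "Secondary measures will include teacher ratings of ADHD and disruptive behavior/impairment".
- **Section 10.2.** The classroom observation system (SBTR), DBD and IRS all stand under the heading "Primary Measures of Behavioral Functioning". The sentence that introduces the teacher behaviour ratings nevertheless says they serve "as indicators of student outcomes as secondary measures to the primary observational measure". The Academic Performance Rating Scale (APRS) has its own heading, "Primary Measures of Academic Functioning".
- **Section 17.1, Aim 1.** "Measures of primary outcome will be observations of classroom behavior and teacher ratings of academic performance". Then: "Measures of secondary outcome will include teacher ratings of symptoms and impairment related to ADHD".

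Section 17.1 also applies BH throughout, across outcomes, without saying which tests form a family. No section says which list prevails.

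**The concern.** The primary list fixes what the trial may put in its headline. Here the endpoint section and the analysis section give different lists, and both are current text. If the measures agree, nothing is lost. If they do not, the same data can support a positive primary conclusion under one section and not under the other, and the choice could be made after the results are seen.

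The two lists also differ in kind. Four of the five instruments in 2.1 are teacher ratings, against one of two in 17.1. Section 10.1 requires the rating teacher in the Daily Report Card (DRC) arm to attend all consultant meetings, so that teacher knows the assignment. The list chosen therefore decides how far the headline rests on unblinded ratings.

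**Working it through.** **1. The sections side by side**

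| Measure | 2.1 | 3.1 | 10.2 heading | 10.2 text | 17.1 |
|---|---|---|---|---|---|
| SBTR observations | primary | tier not stated | primary | primary | primary |
| APRS | primary | tier not stated | primary | – | primary |
| DBD (teacher) | primary | secondary | primary | secondary | secondary |
| IRS (teacher) | primary; impairment also listed as secondary | secondary | primary | secondary | secondary |
| BASC-2 | primary | not named | not named | not named | not named |

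SBTR and APRS are primary in both 2.1 and 17.1. DBD and IRS are in conflict. BASC-2 is undefined outside 2.1.

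**2. The plan's own power figure.** Section 17.2 gives N = 71 for power 0.80 at d = 0.50 with covariates explaining 45% of variance. Alpha is not stated; I assume 0.05 two-sided. Total N = 4 × (1 − 0.45) × (1.960 + 0.842)² / 0.50² = 69.1, or 70 in equal arms; the exact t calculation gives 72. The stated 71 is reproduced, as a single-test figure. At N = 216, power for one test at d = 0.50 is 0.999, and 0.991 even at 0.05/5. Sample size is not the problem.

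**3. The BH family alone can change a result.** Take p = 0.024 for observations and 0.20, 0.30, 0.40 and 0.50 for APRS, DBD, IRS and BASC-2. In a family of two the smallest p is compared with 0.05 × 1/2 = 0.025, and observations are rejected. In a family of five it is compared with 0.05 × 1/5 = 0.010, and nothing is rejected at any rank.

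**4. Illustration of the tier conflict.** From the plan: N = 216, R² = 0.45. Assumed: BH at 0.05 two-sided within each list; success counted only in favour of DRC; correlation 0.3 to 0.7 among teacher ratings and 0.1 to 0.3 between SBTR and teacher ratings; the effect patterns below. Each test statistic has mean d × √(216/4) / √0.55, which is 2.973 at d = 0.30 and 4.954 at d = 0.50. There were 200,000 simulated trials per setting. The any-primary and all-primary rules are mine; the plan states neither.

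| Assumed effects | Rule | 2.1 list | 17.1 list |
|---|---|---|---|
| All d = 0.50 | any | >99.9% | >99.9% |
| All d = 0.50 | all | 99.3-99.4% | 99.7% |
| DBD, IRS, BASC-2 0.30; SBTR, APRS 0 | any | 84-92% | 2.4-2.5% |
| SBTR, APRS 0.30; others 0 | all | under 0.5% | 72-73% |
| SBTR, APRS 0.50; others 0.30 | all | 65-72% | 99.7% |

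In the third row, dropping BASC-2 from the 2.1 list gives 81-87%. Judging the 17.1 measures inside one BH family of five gives 3.7-3.8%.

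**5. Hand check of the third row.** On the 17.1 list both effects are zero, so BH rejects something about 5% of the time, half of it in favour of DRC: 2.5%. On the 2.1 list, if the three ratings were independent, power for each at 0.01 is Φ(2.973 − 2.576) = 0.654, so success is at least 1 − 0.346³ = 0.959. If they were perfectly correlated, all three must reach 0.05 × 3/5 = 0.03, which gives Φ(2.973 − 2.170) = 0.789. The simulated 84-92% lies between.

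**The case against.** The strongest reply is that the plan never speaks of the trial meeting its primary endpoint. Section 17.1 fits a separate model to each outcome and controls false discovery across outcomes. If all outcomes form one BH family, tier labels change no adjusted p-value, only the headline. The any and all rules, and BH within each list, are constructions of this review. The large swings need assumed patterns, two of them with effects of exactly zero. At d = 0.50, the effect size used for Aim 1, the lists agree.

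Most of this stands, and it limits the size of the point. It does not remove it. The family is undefined, so the one-family reading is only one possibility, and the headline is exactly what a primary label governs. Section 17.2 claims about 0.50 or more for the majority of outcomes, not for all.

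Several stronger readings are tempting and are not supported:

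- **Inflated false positives.** For a fixed family, BH keeps the chance of any rejection at about 5% or less when no outcome has an effect. The problem is the choice of family and headline.
- **2.1 is always the lenient list.** It is lenient in the third row of the simulation and strict in the last two.
- **BASC-2 is demoted elsewhere.** No section does so. Section 10.3 refers to a separately submitted table of measures that is not available here.
- **SBTR teacher praise and feedback are rival primary scores.** Section 10.2 assigns these to mediators and fidelity. What is missing is the label of the child-behaviour score and how the three May days are combined.
- **SBTR blinding is compromised.** Whether SBTR observers see the DRC or the comparison checklist is a separate question and forms no part of this point.

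**Conclusion.** The contradiction is in the current text and needs no modelling to see. Section 2.1 and one heading in 10.2 make DBD and IRS primary; 3.1, the 10.2 text and 17.1 make them secondary; 2.1 also lists impairment as secondary. BASC-2 has no tier outside 2.1, the BH family is open, and no section has precedence. The plan is wrong as written on this point and should be corrected.

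The practical size depends on whether the measures disagree. It is negligible if every outcome has d = 0.50. It can decide the headline if they diverge: 84-92% against about 2.5% in the illustrated case. Those percentages rest on assumed effects, assumed correlations and an any-primary rule that the plan does not state. They show what could happen and do not estimate a likely error.

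**What to change.** Use one primary list in 2.1, 3.1, 10.2 and 17.1. Aligning with 17.1 is the natural choice, because SBTR observations and teacher-rated APRS are primary in both 2.1 and 17.1.

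- Make DBD, IRS and the other teacher behaviour ratings secondary, and correct the behavioural heading in 10.2.
- State the tier of BASC-2 or remove it from 2.1. State the tier of the IEP goal rating.
- State that the behavioural and academic claims are made separately, with BH across the two primary tests and separately across the secondary list.
- Name one score per primary instrument: for example, SBTR total student rule violations averaged over the three May observations, and one APRS factor.
- Before choosing the APRS factor, reconcile its description in 10.2. Academic Productivity has 7 items and Academic Success 12, on a five-point scale. If the points run from 1 to 5, the maxima are 7 × 5 = 35 and 12 × 5 = 60, yet the text gives 5-60 for Productivity and 5-35 for Success.

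Settle this before any between-arm outcome analysis, including the preliminary analyses that 19.1 plans after each funded year. Unblinding is not a usable milestone, since section 10.1 has staff and families told the assignment.

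The cost is a wording amendment, with no new data and no change in sample size. The downside is that symptom and impairment ratings cannot carry the headline claim, as 17.1 already implies.
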